1 PROTOCOL SUMMARY

1.1 SYNOPSIS

Title: A multi-center, randomized, double blind, parallel-arm, placebo controlled trial of mepolizumab for treatment of adults and adolescents with active eosinophilic esophagitis and dysphagia-predominant symptoms

Study Description: This multi-center, randomized, double blind, parallel-arm, placebo controlled trial will determine whether mepolizumab is more effective than placebo for improving symptoms of dysphagia and decreasing esophageal eosinophil counts in adults and adolescents with active eosinophilic esophagitis after an initial 3-month treatment course and will also assess the impact of an additional 3-months of treatment.

Objectives: Primary Objectives:

1. To determine whether mepolizumab is more effective than placebo for improving symptoms of dysphagia as measured by the validated Eosinophilic Esophagitis Symptom Activity Index (EEsAI) in adults and adolescents with active eosinophilic esophagitis after a 3-month treatment course.
2. To determine whether mepolizumab is more effective than placebo for decreasing esophageal eosinophil counts in adults and adolescents with active eosinophilic esophagitis after a 3-month treatment course.

Secondary Objectives:

1. To determine predictors of symptomatic and histologic response to mepolizumab treatment, including potential biomarkers.
2. To assess durability of symptomatic and histologic response to mepolizumab after 6 months of treatment in patients initially randomized to the active medication (this includes a 3-month blinded second phase of treatment).
3. To assess histologic response to a lower dose of mepolizumab treatment in patients initially randomized to the placebo arm (this will be in a 3-month blinded second phase); symptom response will also be assessed in this phase.
4. To assess safety of mepolizumab over 3 and 6 months of treatment (this includes both 3-month study phases).

Outcomes:

Primary Outcome:

1. Mean change in dysphagia as measured by the EEsAI score (7-day recall) from baseline to 3-months post-treatment.

Secondary Outcomes:

1. Proportion of patients who have clinical remission as defined by an EEsAI score of ≤ 20 .
2. Proportion of patients who have a clinical response, as defined by an EEsAI score decrease of ≥ 20 points.
3. Absolute peak eosinophil count (measured in eos/hpf) after 3-months of treatment.
4. Levels of histologic response after 3-months of treatment including < 15 , ≤ 6 , and ≤ 1 eos/hpf.

[figure not shown]
5. Mean change in severity of endoscopic findings as measured by the EoE Endoscopic Reference Score (EREFS) from baseline to 3-months post-treatment.
6. Mean change in the Straumann Dysphagia Instrument (SDI) from baseline to 3-months post-treatment.

Prespecified Exploratory Outcomes

1. Mean change in peripheral blood eosinophil levels from baseline to 3-months post treatment.
2. For patients initially randomized to active medication, the same set of outcomes (as listed above) will be assessed after 6 months of treatment.
3. For patients initially randomized to placebo, a paired analysis will be conducted to compare month 6 to month 3 outcomes.
4. For the same set of outcomes (as listed above), 3-month data for patients initially randomized to active medication (300mg monthly) will be compared to 6 month data for patients initially randomized to placebo and who have completed 3-months of 100mg monthly. This will provide a comparison of the 300mg to the 100mg dose.
5. Adverse events and safety during all time points in the study.

Study Population:	72 adult and adolescent patients with active EoE as measured by both symptomatic and histologic severity.
Phase:	2
Description of Sites/Facilities Enrolling Participants:	4 United States sites. Competitive enrollment.
Description of Study Intervention:	Arm 1: Mepolizumab 300 mg SQ monthly for 6 months. Arm 2: Placebo SQ monthly for 3-months followed by mepolizumab 100mg SQ monthly for 3 months. (Note that both arms are blinded for the entire 6 months)
Study Duration:	3 years
Participant Duration:	10 months

1.2 SCHEMA

1.3 SCHEDULE OF ACTIVITIES (SOA)

Visit	Screening/ Baseline ¹ -49 days ¹⁰	Randomization Month 0	Month 1 (+/- 5 days)	Month 2 (+/- 5 days)	Month 3 (+/- 5 days)	Month 4 (+/- 5 days)	Month 5 (+/- 5 days)	Month 6 (+/- 5 days)	Month 8 (+/- 5 days)	Early Termination ⁶	30 Day Phone Call ⁷ 30 days after study discontinuation (+/- 5 days)
Procedure											
Informed consent	X										
Demographics	X										
Medical history	X										
EGD with biopsy and EoE Endoscopic Reference Score (ERES)	X ²				X			X		X	
EEsAI	X		X	X	X	X	X	X	X	X	
Dysphagia Symptom Screening Questionnaire	X										
Patient Global EoE Assessment	X				X			X		X	
PGIC and PGIS					X			X		X	
VAS Assessment	X ⁸				X ⁸			X ⁸	X ⁸	X ⁸	
Complete blood count (CBC) w/ differential ⁹	X ³		X	X	X	X	X	X	X	X	
Serum/anti-IL 5 antibodies	X				X			X	X	X	
Physical exam	X				X			X		X	
Vital signs	X	X	X	X	X	X	X	X		X	
Pregnancy test	X	X	X	X	X	X	X	X	X	X	
Concomitant medication review	X	X	X	X	X	X	X	X	X	X	
Adverse event review and evaluation	X	X	X	X	X	X	X	X	X	X	X
48-hour adverse event review and evaluation		X ⁴	X ⁴	X ⁴	X ⁴	X ⁴	X ⁴				
Randomization		X									
Straumann Dysphagia Index (SDI)	X ⁵	X ⁵	Weekly					X ⁵	X ⁵	X ⁵	
Administer study drug		X	X	X	X	X	X				
Complete Case Report Forms (CRFs)	X	X	X	X	X	X	X	X	X	X	X

¹Screening can occur over multiple days, however blood labs should be obtained on the day of the screening EGD if possible. Screening assessments will also be used for baseline measures and will not be repeated at randomization unless indicated above. For the purposes of statistical analysis, this study will consider baseline at the point when symptoms are assessed prior to the study drug being given.

²Subjects must be deemed eligible per EEsAI score and dysphagia questionnaire prior to undergoing the screening EGD. Sites must obtain approval from the lead site (UNC) prior to performing the screening EGDs. Recent historical EGD information may be allowable in lieu of repeating endoscopic procedures. [name] will review requests to use historical EGDs in lieu of the screening EGD on a case-by-case basis.

³Screening CBC with differential will be analyzed by local laboratory. Subsequent CBC will be sent to Central Lab for processing.

⁴Subjects will be contacted 48 hours (+ 1 week) after administration of study drug to assess for adverse events via IRB approved methods.

⁵SDI is completed at the screening/baseline visit, month 6, month 8, and early termination (if applicable). Weekly SDIs are completed by the subject at home beginning one week from randomization until the month 6 visit, where the SDI will be completed during the visit. See section 8.2.1

⁶Subjects who prematurely exit the study will be asked to complete an early termination visit.

Visit	Screening/ Baseline ¹ -49 days ¹⁰	Randomization Month 0	Month 1 (+/- 5 days)	Month 2 (+/- 5 days)	Month 3 (+/- 5 days)	Month 4 (+/- 5 days)	Month 5 (+/- 5 days)	Month 6 (+/- 5 days)	Month 8 (+/- 5 days)	Early Termination ⁶	30 Day Phone Call ⁷ 30 days after study discontinuation (+/- 5 days)
⁷ 30-day follow-up is completed 30 days after subject is exited from study, including early termination.											
⁸ A VAS should be completed if subject reports any allergic diseases. VAS should be completed for each allergic condition applicable.											
⁹ Unscheduled visits can be scheduled in cases where study assessments need to be re-assessed. Notification and approval from the lead site should be considered before scheduling these visits.											
¹⁰ Subjects have up to 49 days from screening/baseline prior to randomization to remain eligible for study participation.											

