5 STUDY POPULATION

5.1 INCLUSION CRITERIA

In order to be eligible to participate in this study, an individual must meet all of the following criteria:

1. Age 16-75*
2. Diagnosis of EoE as per consensus guidelines (including PPI non-response**).^{2, 43}
3. Active eosinophilia on esophageal biopsy, with a peak count of least 15 eos/hpf from at least one esophageal level.***
4. Biopsies from the stomach and duodenum that have ruled out alternative etiologies in all children and in adults with abnormal endoscopic findings or when other gastric or small intestinal conditions are clinical possibilities. If these samples have been obtained during a previous endoscopic evaluation and in the judgement of the site-Investigator the patient has not had a clinically significant change that would merit repeat gastric/duodenal biopsies, then prior normal gastric and duodenal biopsies are acceptable to exclude alternate etiologies.
5. Active symptoms of dysphagia with more than 3 episodes of dysphagia over a period of 2 weeks during the screening period, and an Eosinophilic Esophagitis Symptom Activity Index (EEsAI; see below for details) score of ≥ 27 at baseline.****
6. Able to read, comprehend, and sign consent form.
7. Have maintained a stable diet for 6 weeks prior to enrollment.*****
8. Able to maintain a stable diet throughout the duration of the study period. *****
9. Female subjects of childbearing potential who have had their first menses agree to use a highly effective method of birth control during the study and for 30 days after the last dose of study drug. Female subjects with reproductive potential who are using systemic contraceptives (e.g., oral contraceptives, injectable contraceptives, implantable/insertable hormonal contraceptive products, or transdermal patches) to prevent pregnancy must have stable use for ≥ 28 days prior to screening. See section 5.3 for additional details.

* The rationale for this criterion is that adolescents and adults with EoE have a very similar clinical presentation with dysphagia-predominant symptoms.²¹ If we were to enroll younger patients there would be few who would meet the dysphagia threshold, and the symptom metric we will use was not validated in younger patients.⁴² Patients of any age can have EoE, but in patients above the age of 75 malignancy is a concern with clinical symptoms of dysphagia, and EoE becomes less common.¹²

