8 STUDY ASSESSMENTS AND PROCEDURES

8.1 SCREENING AND BASELINE

During screening/baseline, the following assessments will be completed. Not all are used to determine eligibility. Baseline symptoms are gathered during the screening visit and used as baseline measurements for this study.

1. Informed consent
2. Demographics
3. Medical history
4. EGD with biopsy and EoE Endoscopic Reference Score (EREFs)*
5. EEsAI*
6. Dysphagia Symptom Screening Questionnaire*
7. Patient Global EoE Assessment*
8. VAS (Visual Analog Scale) Assessment; if applicable for subjects with known allergic diseases
9. CBC with differential*
10. Serum/anti-IL 5 antibodies*
11. Physical exam*
12. Vital signs*
13. Urine pregnancy test*
14. Concomitant medication review
15. Straumann Dysphagia Index (SDI)
16. Adverse event review and evaluation
17. Completion of CRFs

*If eligible, then these assessments performed during the screening phase will also be used for baseline and do not need to be repeated at randomization.

All screening and baseline assessments should be completed prior to and within 49 days of randomization.

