8.1.1 SYMPTOM ASSESSMENT FOR ELIGIBILITY

Symptom assessment for eligibility will occur via completion of both the EEsAI questionnaire and a dysphagia questionnaire. These questionnaires should be completed during the screening phase after informed consent is obtained and prior to the screening endoscopy.

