8.7 SAFETY AND OTHER ASSESSMENTS

The following safety assessments will be performed:

1. Pregnancy test performed at every study visit for women of childbearing potential
2. Symptom assessment at every study visit
3. Adverse event assessment at every study visit, including injection site reactions
4. Vital signs as noted above with study drug administration
5. Adverse event review and assessment completed 48 hours after study drug administration
6. Month 8 visit occurring 3-months after last dose of study drug.
7. 30-day end of study phone call after study completion or early termination.

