9.4.2 ANALYSIS OF THE PRIMARY EFFICACY OUTCOMES(S)

The primary outcome will be the mean change in dysphagia as measured by the EEsAI score (7-day recall) from baseline to 3-months post-treatment. Patients will complete this measure at screening (baseline), and then every month throughout the study when they come for their medication injection. This study will consider baseline at the point when symptoms are assessed prior to the study drug being given.

We are focusing on symptoms as the primary outcome as this is the key clinical metric for a PRO-measured treatment response.⁴¹ The EEsAI is a validated and responsive PRO, developed by an international team of EoE experts, that measures dysphagia frequency, dysphagia severity, and food avoidance/modification behaviors, in patients with EoE.^{42, 45-47} It has now been used in several clinical trials, including recently published abstract data emphasizing the responsive nature of this instrument.⁴⁸ In the first, 59 subjects were randomized to receive an or disperisble budesonide tablet and 29 to placebo.⁵¹ A total of 30 patients (59%) in the active arm achieved an EEsAI score of ≤ 20 compared to just 2 patients (7%) in the placebo arm ($p < 0.0001$). In the second study, which was a study of the anti-IL-4 α receptor blocker dupilumab, EEsAI was measured in a subset of patients had EEsAI.⁴⁹ The 17 patients who received active treatment had a 36% decrease in the EEsAI score compared to an 11% decrease in the 13 patients who received placebo ($p = 0.085$). These new data support the use of the EEsAI as a primary outcome. The EEsAI score can range from 0 to 100, with higher scores indicated more severe symptoms; a decrease of 20 points is felt to be a meaningful clinical response, and scores ≤ 20 represent clinical remission.

For the primary outcome, the mean change in dysphagia from baseline to 3-months post-treatment (as measured by the EEsAI score with 7-day recall) will be compared between the mepolizumab and placebo groups using analysis of covariance. In discussion with the study statistician, the main factor that we will include in the primary analysis is the baseline EEsAI score, though in the exploratory analyses we will assess trial site. We will also include the stratification factor (prior steroid response as a covariate as appropriate in the analyses (see below as well).

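### The baseline EEsAI for the primary outcome is the eligibility score, taken up to 49 days before the first dose; a pre-dose score at month 0 would be a cheap gain in precision

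*Combined protocol and SAP*

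**What the plan says.** The primary outcome in section 1.1 is "Mean change in dysphagia as measured by the EEsAI score (7-day recall) from baseline to 3-months post-treatment". Under section 9.4.2 it is compared by analysis of covariance, where "the main factor that we will include in the primary analysis is the baseline EEsAI score". One score is thus both the start of the change and the main covariate.

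That score is the one used for entry. Section 5.1 requires an EEsAI "score of ≥ 27 at baseline", and section 8.1.1 says of the EEsAI and the dysphagia questionnaire: "These questionnaires should be completed during the screening phase after informed consent is obtained and prior to the screening endoscopy". On its age, section 8.1 says: "All screening and baseline assessments should be completed prior to and within 49 days of randomization". Footnote 10 of the schedule gives the same limit.

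It is not repeated before dosing. Footnote 1 of section 1.3 reads "Screening assessments will also be used for baseline measures and will not be repeated at randomization unless indicated above". The EEsAI row of the schedule has no mark at month 0, and the list for the randomisation visit in section 8.2, where the first injection is given, omits it.

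Two other passages touch on timing. Section 9.4.2: "Patients will complete this measure at screening (baseline), and then every month throughout the study when they come for their medication injection". Section 8.7, in a list of safety assessments: "Symptom assessment at every study visit".

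**The concern.** With a 7-day recall and a 49-day window, the baseline can describe days -56 to -49 before the first dose, whereas each later EEsAI visit has a window of 5 days either side. Two consequences follow.

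First, ANCOVA gains precision only to the extent that the covariate predicts the month 3 score. A score several weeks old, with its range cut at 27, may predict less well than one taken at the dosing visit.

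Second, patients enter because this score was high enough. Some of the fall from it would occur without any treatment, and part of that before the first injection. The fall is counted in the mean change within each arm and in the secondary outcome of a decrease of at least 20 points, which section 9.4.3 tests by chi-square without adjustment for baseline.

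**Working it through.** **1. The plan's own figure.** Inputs from section 9.2: difference 17 (15 against 32), SD 20, alpha 0.05 (two-sided, section 9.4.1), power 0.90.

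n = 2 × [20 × (1.960 + 1.282) / 17]² = 29.1, so 30 per arm. Power at 30 per arm is 0.909 (normal) or 0.899 (t-based). The stated 30 reproduces, and it takes no credit for a covariate.

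**2. Power with the screening covariate.** Let r be the correlation of baseline with month 3. The documents do not give it, so it is an assumption throughout.

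- If SD 20 is that of the score, the residual SD is 20 × √(1 − r²). Power at 30 per arm is 0.909 at r = 0, 0.932 at 0.3, 0.949 at 0.4, 0.967 at 0.5 and 0.984 at 0.6.
- If SD 20 is that of the change, the residual SD is 20 × √((1 + r)/2). Power is at least 0.946 for r from 0 to 0.7.

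A weak covariate forgoes a gain; it does not take power below what was planned.

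**3. Bias and type I error.** Simulation with entry at screening EEsAI of at least 27, 30 per arm, about 4,000 trials per scenario. Assumed: mean 45 or 55, SD 20, screening-to-month-0 correlation 0.5 to 0.8. Before selection, the correlation with month 3 is 0.25 to 0.5 for screening and 0.4 to 0.6 for month 0.

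| Covariate | Type I error | Estimate of a true 17 | Power |
|---|---|---|---|
| Screening | 0.048–0.054 | 16.9–17.1 | 0.907–0.960 |
| Month 0 | 0.045–0.054 | 17.0–17.1 | 0.934–0.981 |

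Scenario by scenario, month 0 adds 2.0 to 3.4 points of power.

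**4. Precision if month 0 predicts better.** SE ratio = √[(1 − r₁²)/(1 − r₀²)], with r₀ = 0.4 for screening.

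- r₁ = 0.5: √(0.75/0.84) = 0.945, a 5% fall, equal to 0.84/0.75 − 1 = 12% more patients.
- r₁ = 0.6: √(0.64/0.84) = 0.873, a 13% fall, equal to 31% more patients.

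**5. Precision if month 0 predicts no better.** With two scores that each correlate r with month 3 and ρ with each other, R² = 2r²/(1 + ρ).

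| r | ρ | R² | SE ratio, both scores against one |
|---|---|---|---|
| 0.4 | 0.8 | 0.178 | √(0.822/0.84) = 0.989 |
| 0.4 | 0.5 | 0.213 | √(0.787/0.84) = 0.968 |
| 0.5 | 0.8 | 0.278 | √(0.722/0.75) = 0.981 |
| 0.5 | 0.5 | 0.333 | √(0.667/0.75) = 0.943 |

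The gain is about 1 to 6%. With N = 60 patients and p covariates, chance imbalance inflates the variance by about 1 + p/(N − p − 3). Going from p = 1 to p = 2 multiplies it by (57/55)/(57/56) = 56/55, or 0.9% on the SE. Net, the gain runs from nearly nothing to about 5%.

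**6. Regression to the mean.** Expected fall with no treatment = (1 − retest correlation) × SD × φ(a)/(1 − Φ(a)), with a = (27 − mean)/SD. All inputs are assumed: mean 45–55, SD 16–20, retest correlation 0.5–0.8.

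- Smallest: mean 55, SD 16, correlation 0.8: 0.2 × 16 × 0.090 = 0.3 points.
- Largest: mean 45, SD 20, correlation 0.5: 0.5 × 20 × 0.326 = 3.3 points.

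In the simulation of step 3, the share of patients with a fall of at least 20 points and no treatment effect was 0.171–0.249 from screening and 0.140–0.198 from month 0. That is 3 to 5 percentage points more, in both arms.

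**The case against.** The strongest reply is that nothing is broken. The baseline definition is consistent, randomisation balances regression to the mean, and the sample size never relied on the covariate. The order is also deliberate: symptoms must qualify before the endoscopy, and biopsies then go to a central laboratory. Sections 4.1 and 6.5.1 bar changes in diet, PPI dose and steroids from consent, which limits drift. The documents give neither the typical gap nor the stability of the EEsAI, so 49 days is a ceiling, and every figure for the gain is assumed. All of this stands, and it keeps the point to an improvement in precision.

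A reader might infer that the documents contradict each other on when baseline is measured. They do not. Every passage that names a visit for baseline symptoms names screening (sections 5.1, 5.5, 8.1, 8.1.3 and 8.1.4). The sentence in section 9.4.2 puts screening first and the monthly visits after it, which matches the schedule. Section 8.7 does not name the EEsAI; its wording is merely loose, since no EEsAI is scheduled at month 0.

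A reader might also infer that the primary comparison is biased or underpowered. Steps 2 and 3 show neither.

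A further objection concerns the remedy. Making month 0 the new baseline only for later patients would mix two definitions in one endpoint. It would also let a patient start at 20 or below, already in remission by the plan's definition; from below 20, a fall of 20 points is impossible. That objection is right, and it shapes the fix.

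**Conclusion.** The point holds as a cheap improvement. The only pre-dose EEsAI is the qualifying score; it may be up to 49 days old at the first dose, and it serves as both the start of the change and the main covariate. The arm difference is unbiased, type I error is held, and power stays at about 0.90 or above under either reading of the SD.

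What is given up is precision: 5 to 13% of the standard error if month 0 correlates 0.5–0.6 with month 3 against 0.4 for screening, and about 1 to 6%, before the degree-of-freedom cost, if it is no better a predictor. These correlations are assumptions. At the unfavourable end the net gain is close to zero.

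The results most exposed to regression to the mean are the within-arm changes and the 20-point response rates, which are inflated in both arms. They should not be read as treatment response on their own.

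**What to change.** - Add an EEsAI before dosing at month 0 to the schedule (section 1.3) and to the list in section 8.2.
- Keep the screening score for eligibility and as the defined start of the change score for all patients, so that one baseline definition applies throughout.
- If the month 0 score is collected from the first patient, prespecify it in section 9.4.2 as an additional covariate in the primary ANCOVA, alongside screening. If it is introduced later, use it in a sensitivity analysis only.
- Report the response of at least 20 points from both starting points.
- Align the symptom-assessment line in section 8.7 with the schedule.

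The cost is one short questionnaire at a visit already held, a schedule amendment and one model degree of freedom.

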2 INTRODUCTION

2.1 STUDY BACKGROUND AND RATIONALE

Eosinophilic esophagitis (EoE) is a Th2-mediated allergic disease whereby abnormal infiltration of eosinophils into the esophageal mucosa leads to dysphagia, progressive esophageal stenosis, and food impaction.¹⁻³ First described in the late 1970s⁴ and initially felt to be rare,⁵ the incidence has increased more than four-fold in the last ten years.⁶⁻⁹ Because EoE is chronic, the prevalence is also increasing and is now estimated to be at least 1 in 2000.^{6, 7, 10-13} Overall, between 5% and 23% of patients undergoing endoscopy for dysphagia will have EoE,¹⁴⁻¹⁸ and more than 50% of patients presenting to an emergency room with food impaction are now diagnosed with EoE.^{3, 19} Because of this large burden of disease, health care costs of EoE are also significant, accounting for more than \$1 billion annually.²⁰

There is currently an urgent need for new treatments for EoE. There are no medications that are Food and Drug Administration (FDA)-approved for EoE,²¹ and the current pharmacologic standard of care, swallowed topical steroids, are suboptimal. Topical steroids are asthma preparations such as fluticasone or budesonide that are swallowed rather than inhaled,²²⁻²⁶ and because a pulmonary-specific medication system is being used to attempt to coat the esophagus to provide an anti-inflammatory effect, results are lacking. For example, up to 50% of patients do not have histologic response to these medications,²⁷ and emerging data suggest that the effect of steroids in responders may wane over time.²⁸ Moreover, these medications are not specific to the known pathogenesis of EoE.²⁹

The cytokine IL-5 has been shown to play a major role in EoE pathogenesis.^{30, 31} IL-5 is increased in patients with EoE, leads to production of IL-13, which in turn stimulates the esophageal epithelium to produce eotaxin-3, a potent chemokine that recruits eosinophils to the esophagus.³² In experimental models of EoE, blocking IL-5 attenuates the disease state, whereas overexpression of IL-5 creates an EoE-like phenotype.^{31, 33} Mepolizumab is a recombinant monoclonal antibody that binds IL-5 and has been demonstrated to be highly effective in eosinophilic diseases such as hypereosinophilic syndrome (HES),³⁴ eosinophilic asthma,^{35, 36} and most recently eosinophilic granulomatosis with polyangiitis.³⁷ Because of its mechanism of action, mepolizumab is a highly promising therapeutic agent for EoE, and has previously been studied in this condition. A small randomized clinical trial (RCT) in 11 adults showed a good histologic effect (55% decrease in mean tissue eosinophil levels in the mepolizumab arm vs 7% decrease in the placebo arm), but variable symptom response.³⁸ A larger RCT examining three dosing regimens in 59 children also showed a good histologic effect (peak eosinophil count decreased from 118 eosinophils per high-power field [eos/hpf] to 24 eos/hpf in the 2.5 mg/kg arm), but symptoms were relatively mild at baseline and there was no clear overall trend towards improvement.³⁹ Of note, similar histologic and symptomatic discordance was also observed in a clinical trial of children treated with a different anti-IL-5 antibody.⁴⁰

The counterintuitive results of these studies, where a moderate to robust histologic response was observed in the absence of symptom improvement, can be explained by study design issues. Both studies of mepolizumab used non-validated symptom measures, and a symptom threshold for entry was not required. In addition, the pediatric study utilized a multisymptom instrument, so improvements in one symptom may have been lost if other symptoms worsened. Moreover, both of these studies were performed prior to the strong understanding of best practices for clinical trial conduct that we now have in the field.⁴¹ This includes the need to focus on a single primary symptom, enroll a homogeneous set of patients with highly active disease, account for esophageal remodeling (severe esophageal strictures or narrowing), and restrict baseline esophageal dilation. These latter two points are particularly important

in studies of adults and adolescent with dysphagia-predominant symptoms. In the presence of a stricture that is not dilated, symptoms of dysphagia can persist even with resolution of eosinophilic inflammation. In contrast, symptoms can improve after dilation regardless of persistent esophageal eosinophilia.

Given the strong biologic rationale for anti-IL-5 therapy, advances in knowledge about EoE, increased understanding about optimal RCT design for EoE therapies, and the development and validation of EoE-specific patient-reported outcomes (PRO), it is imperative to revisit mepolizumab treatment for EoE using an optimized clinical trial design and a validated PRO. Our overall hypothesis is that mepolizumab will improve symptoms of dysphagia, as measured by a validated PRO, in adolescents and adults with EoE, as well as improve esophageal eosinophilia, as compared to placebo.

